2. SYNOPSIS

Name of Sponsor/Company: Caliway Biopharmaceuticals Co., Ltd.						
Name of Investigational Product: CBL-514						
Name of Active Ingredient: Curcumin and trans -resveratrol						
Protocol Number: CBL-0203						
Title of Study: A Phase 2 Study to Evaluate the Pharmacokinetic Profile of CBL-514 Injection in Healthy Volunteers						
Phase of Development: Phase 2						
Objectives: Primary: 
 To evaluate the pharmacokinetics (PK) profile of the components of CBL-514 in plasma following administration of CBL-514 into subcutaneous fat. Secondary: 
 To identify and assess the metabolites of CBL-514 in plasma following administration of CBL-514 into subcutaneous fat. To evaluate safety and tolerability of CBL-514 administered into subcutaneous fat. 						
Methodology: 
This is a Phase 2 study to evaluate the safety, tolerability, PK and metabolite profile of CBL-514 injection at the maximal use dosage.
 
This Phase 2 study has an open-label and single course design. A total of 10 adult participants, composed of 5 females and 5 males, will be enrolled in a single cohort. Each participant will receive a single course of treatment with CBL-514 800 mg on the abdomen (administered as multiple subcutaneous injections) on Day 1 only.
 
The dosing scheme is presented in the table below.
						
Table S1: Dosing Scheme						
Treatment Area	Dose level (mg/cm ²)	Injection volume per 7.5 cm ² grid (mL)	Administration			
			No. of injections	Total injection volume (mL)	Total CBL-514 (mg)	
Abdomen	2.0	[REDACTED]	[REDACTED]	160	800	Curcumin [REDACTED]
						Resveratrol [REDACTED]
Note: The concentration of CBL-514 is [REDACTED] mL.						

In accordance with the maximal use of CBL-514, [REDACTED] will be administered to each participant in order to reach the required injection dosage of 800 mg.

Oral analgesia as per standard of care will be administered to participants approximately 1 hour prior to IP administration. Topical anesthesia cream will be applied to the treatment area, followed by local anesthesia injection, both as per standard of care. If needed, participants may undergo ice compress immediately prior to IP injection. The IP administration should be completed within 60 minutes.

Participants will remain in the clinic for at least 24 hours after dosing. During this time, blood samples will be collected to determine the PK and metabolites profile of curcumin and resveratrol. PK samples will be collected from all 10 participants. Of these 10 participants, 6 participants (the first 3 females and the first 3 males enrolled) will have additional samples collected for metabolite assessment.

Prior to discharge on Day 2, at the discretion of Investigator, participants may be prescribed analgesics and/or antihistamines to treat injection site reactions.

Follow-up will be performed at Week 2 and Week 4 to assess safety.

An Early Termination visit will be planned for any participant who receives treatment and is withdrawn from the study earlier than scheduled.

Participants who cannot meet the dosing compliance specified in [Section 10.5](#) will be withdrawn and will not continue the collection of PK samples post-dose. Safety assessment post-dose on Day 1 will be completed before discharge and an Early Termination visit will be planned.

Number of Participants:

10 (5 females and 5 males).

Inclusion Criteria:

A participant can participate in the study only if all the following criteria are met:

1. Male/female aged 18 years to 64 years old (at Screening), inclusive.
2. Body mass index (BMI) > 18.5 and $< 35 \text{ kg/m}^2$ and body weight $\geq 50 \text{ kg}$ at Screening and Day 1.
3. Participant has sufficient subcutaneous fat thickness of at least 3.00 cm (30.0 mm) measured by caliper skinfold method surrounding the center of localized area of treatment as well as the left and right edges of treatment area at Screening and Day 1.
4. Voluntarily signs the Informed Consent Form (ICF) and, in the opinion of the Investigator or delegate, is physically and mentally capable of participating in the study, and willing to adhere to study procedures, including food and drink restrictions.

Exclusion Criteria:

A participant who meets any of the following exclusion criteria must be excluded from the study:

1. Women of childbearing potential (WOCBP) who are not willing to commit to an acceptable contraceptive regimen from the time of Screening and throughout study participation until 90 days after the last IP dose, or who are currently pregnant or lactating. Male participants who are not willing to commit to an acceptable contraceptive method. For details on contraception, refer to [Section 9.3.3](#). Female participants who are not WOCBP are not required to use contraception.

- * Not WOCBP is defined as females who have been surgically sterilized (hysterectomy or bilateral oophorectomy) or who are postmenopausal (defined as at least 50 years, with ≥ 12 months of amenorrhea) with a follicle-stimulating hormone (FSH) > 40 IU/L prior to Screening.
2. Participant diagnosed with coagulation disorders or is receiving anticoagulant/antiplatelet therapy or medications or dietary supplements, which impede coagulation or platelet aggregation.
 3. Participant has hemoglobin A1c (HbA1c) $\geq 9\%$, delayed wound healing, or any diabetic risks which, in the opinion of Investigator, is inappropriate to participate in the study.
 4. Participant has a clinically significant cardiovascular disease and clinically significant abnormal findings in electrocardiogram (ECG).
 5. Participant with active or prior history of malignancies within 5 years before Screening or being worked-up for a possible malignancy. Except adequately treated basal cell carcinoma of skin and in situ squamous cell carcinoma of skin would be eligible as per Investigator's discretion.
 6. Participant with a history of human immunodeficiency virus (HIV)-1 infection, or participants with active HIV infection at Screening with positive HIV antigen/antibody (Ag/Ab) combo test.
 7. Participants with any hepatic medical condition that, in the opinion of the Investigator, would compromise the participant's ability to undergo study procedures and/or interfere with the assessment of the obtained data.
 8. Participants with a history of trypanophobia, the extreme fear of medical procedures involving injections or needles, or who experience vasovagal syncope and faint or pass out at the sight of blood or a needle.
 9. Participant has abnormal skin or local skin conditions at the treatment area, which in the opinion of Investigator, is inappropriate to participate in the study, including but not limited to any of the following:
 - a. Skin manifestations of a systemic disease,
 - b. Cicatricial tissue or any abnormality of the skin or soft tissues on the anticipated treatment area,
 - c. Grade III cellulite (Nürberger and Muller scale, [Nürberger F, 1978](#)) at the area to be treated,
 - d. Skin folding on treatment area when the participant is in the supine position,
 - e. Sensory loss or dysesthesia in the area to be treated,
 - f. Evidence of any cause of enlargement in the area to be treated other than localized subcutaneous fat,
 - g. Tattoos on the area to be treated.
 10. Participant who has the following procedures:
 - a. Previous surgery which caused scar tissues on the anticipated treatment area before Screening or during the study, except laparoscopic surgery and surgery which causes very small scar tissues would be eligible as per Investigator's discretion,
 - b. Liposuction to the region to be treated before Screening or during the study,

- c. Esthetic procedure e.g., cryolipolysis, ultrasonic lipolysis, low-level laser therapy (LLLT), lipolysis injection to the region to be treated within 12 months before Screening or during the study.

11. Participant is undergoing chronic systemic steroid or immunosuppressive therapy.
12. Requiring continual use of the following therapeutic agents during the study: terfenadine, buspirone, fexofenadine, any medication that is known to strongly inhibit or induce CYP enzymes (refer to [Section 24.1](#)), sensitive CYP substrates or drugs with narrow therapeutic index, in the opinion of the Investigator, may affect the evaluation of the study product or place the participant at undue risk.
If a participant needs to use the above-mentioned therapeutic agents during the study for any reason, these therapeutic agents should not be used for at least 2 days prior to dosing and until 1 day post-dose.
13. Unable to receive local anesthesia (e.g., history of hypersensitivity to lidocaine).
14. Participants with known allergies or sensitivities to the IP or its components.
15. Participants with liver cirrhosis or with inadequate liver function at Screening defined as aspartate aminotransferase (AST), alanine aminotransferase (ALT), alkaline phosphatase (ALP), total bilirubin (TBIL), or gamma-glutamyl transferase (GGT) $> 3.0 \times$ upper limit of normal (ULN).
16. Participants with any renal impairment, defined as abnormal serum creatinine, and urea $> 1.5 \times$ ULN or estimated glomerular filtration rate (eGFR) < 90 mL/min/1.73 m².
Participants who are currently on dialysis should be excluded.

Participants with an eGFR ≥ 60 and < 90 mL/min/1.73 m² at Screening should be evaluated by the Investigator to exclude pre-existing renal disease or associated dysfunction. If mild decrease in eGFR is assessed by the Investigator as not clinically significant or not related to dysfunction, the subjects may be eligible upon the Investigator's assessment.
17. Use of other investigational drug or device within 4 weeks prior to Screening.

Withdrawal criteria:

A participant must be removed from the study at any time, if any of the following criteria is met:

- Participant withdraws consent,
- Participant cannot meet the dosing compliance specified in [Section 10.5](#),
- Any other clinical adverse event (AE), medical condition, or situation arises, that in the opinion of the Investigator it would not be in the best interest of the participant to continue participation.

Investigational Product, Dosage and Mode of Administration:

Table S2: CBL-514 Product Details

Name	CBL-514
Active Ingredients	Curcumin and trans -resveratrol
Dosage form	Subcutaneous Injection, [REDACTED]/mL of CBL-514, 20 mL/vial
Pharmacological category	D11AX other dermatological

Duration of Treatment:

The Screening period is 28 days (Day –28 to Day 1).

Each participant will participate in the study for approximately 4 weeks, including an Admission/Baseline visit on Day 1 with an overnight stay until Day 2, and 2 Follow-up visits (2 weeks [in-clinic] and 4 weeks [telephone] post treatment).

Duration of study participation is defined as the period between the day the participant provides written consent and 28 days after dose administration, or until all study required examinations have been completed, whichever is longer or applicable.

Criteria for Evaluation:**Pharmacokinetics:**

- The primary PK endpoint is to evaluate the PK of the components of CBL-514 in plasma following administration of CBL-514 into subcutaneous fat. PK parameters following a single course of administration of CBL-514 will include, but are not limited to the following:

- Maximum analyte concentration (C_{\max})
- Time to C_{\max} (t_{\max})
- Area under the concentration-time curve from time 0 to the last quantifiable concentration (AUC_{0-t})
- Area under the concentration-time curve from time 0 to 24 hours post-dose (AUC_{0-24hr})
- Area under the concentration-time curve from time 0 extrapolated to infinity (AUC_{0-inf})
- Elimination half-life ($t_{1/2}$)
- Apparent total plasma clearance (CL/F)
- Apparent terminal volume of distribution (V_z/F)

- The secondary PK endpoint is to identify and characterize the metabolites of CBL-514 following administration of CBL-514 into subcutaneous fat.

Blood samples for PK and metabolite analysis will be collected at the following time points on Day 1 and Day 2: pre-dose (within 30 minutes prior to scheduled dosing), 1 hour (± 10 minutes), 2 hours (± 10 minutes), 4 hours (± 10 minutes), 5 hours (± 10 minutes), 6 hours (± 10 minutes), 7 hours (± 10 minutes), 8 hours (± 10 minutes), 10 hours (± 10 minutes), 12 hours (± 10 minutes), 18 hours (± 10 minutes), and 24 hours (± 10 minutes) post-dose (from the start of CBL-514 administration).

Safety:

- The safety endpoints are the safety and tolerability following a single subcutaneous dose of CBL-514 as assessed by recording of treatment-emergent adverse events (TEAEs), laboratory assessments, vital signs, ECGs, and physical examinations.

Statistical Methods:

Complete details of the statistical analyses and methods, including data conventions, will be provided in the statistical analysis plan (SAP). The SAP will be finalized before the database is locked.

Descriptive statistics will be used to summarize the safety and PK data. No adjustments will be made for missing or incomplete data.

Analysis Populations**PK Population:**

The PK Population will consist of all participants who receive any amount of IP and have sufficiently evaluable concentration-time profiles of plasma curcumin and/or resveratrol to allow determination of at least one PK parameter among C_{\max} , t_{\max} , and AUC_{0-24hr} . An evaluable PK profile will be determined at the discretion of the pharmacokineticist following examination of participants with

dosing or protocol deviations that could potentially affect the PK profile. The PK Population determination will be done by the study pharmacokineticist post database lock.

The PK Population will be used for PK analyses and the summaries of all PK data. Any participant or data excluded from the analysis will be identified, along with their reason for exclusion, in the clinical study report (CSR).

Metabolites Population:

The Metabolites Population will consist of all participants who receive any amount of IP and have at least one quantifiable concentration of any identified metabolite(s) of curcumin and/or resveratrol.

The Metabolite Population will be used for presenting individual and summary concentrations only without PK analysis and/or PK parameters. Any participant or data excluded from the analysis will be identified, along with their reason for exclusion, in the CSR.

Safety Population:

All participants who receive the IP will be included in the Safety Population. The Safety Population will be used for summaries and listings of safety and tolerability.

Pharmacokinetics Assessment

Plasma concentrations and derived PK parameters for curcumin and resveratrol will be summarized descriptively. Any identified metabolite(s) concentrations of curcumin and/or resveratrol will only be presented for listings and summary without PK analysis and/or PK parameters.

Safety Assessment

All safety assessments, including AEs, laboratory evaluations, vital signs, ECGs, physical examination, and other safety assessments, will be analyzed using the Safety Population.

AEs will be coded using the most current version of the Medical Dictionary for Regulatory Activities (MedDRA®) available at the start of the study. A by-participant AE data listing, including verbatim term, Preferred Term (PT), System Organ Class (SOC), treatment, severity, and relationship to IP, will be provided. The number of participants experiencing TEAEs and number of individual TEAEs will be summarized by SOC and PT. TEAEs will also be summarized by severity and by relationship to the IP.

Observed values and changes from Baseline in clinical laboratory tests and vital signs will be summarized using descriptive statistics. Physical examination findings and ECGs will also be summarized descriptively.

TABLE OF CONTENTS

1.	TITLE PAGE.....	1
	PROTOCOL AUTHORIZATION.....	2
	INVESTIGATOR'S AGREEMENT	3
	PROCEDURES IN CASE OF EMERGENCY	4
2.	SYNOPSIS	5
3.	TABLE OF CONTENTS	11
4.	LIST OF ABBREVIATIONS AND DEFINITIONS OF TERMS.....	18
5.	FACILITIES AND PERSONNEL	21
6.	BACKGROUND AND INTRODUCTION	22
6.1.	Introduction.....	22
6.2.	Summary of Nonclinical and Clinical Studies.....	23
6.2.1.	Nonclinical Studies	23
6.2.2.	Clinical Studies	23
6.2.2.1.	Safety and Tolerability	23
6.2.2.2.	Pharmacokinetics	24
6.2.2.3.	Efficacy	25
6.3.	Dosage Rationale	25
6.4.	Participant Population.....	25
6.5.	Summary of Potential Risks and Benefits	26
6.6.	Ethical Principles	26
7.	TRIAL OBJECTIVES AND PURPOSE.....	27
7.1.	Objectives	27
7.1.1.	Primary Objective	27
7.1.2.	Secondary Objective	27
7.2.	Endpoints	27
7.2.1.	Primary Endpoints	27

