9.6. Participant Withdrawal Criteria

In accordance with applicable regulations, a participant has the right to withdraw from the study, at any time and for any reason, without prejudice to their future medical care. If a participant withdraws consent, the date and reason for consent withdrawal should be documented. Participant data will be included in the analysis up to the date of the withdrawal of consent.

A participant must be removed from the study at any time, if any of the following criteria is met:

- Participant voluntarily withdraws consent,
- Participant cannot meet the dosing compliance specified the [Section 10.5](#),
- Any other clinical AE, medical condition, or situation arises, that in the opinion of the Investigator it would not be in the best interest of the participant to continue participation.

If a participant is withdrawn because of an AE, the Investigator must arrange for the participant to have appropriate follow-up care until the AE is resolved or has stabilized. Unresolved AEs will be followed until the last scheduled Follow-up/ET visit or until the Investigator and MM determine that further follow-up is no longer indicated.

If a participant is withdrawn due to a lack of dosing compliance, a clear reason for not completing the treatment must be recorded. The collection of PK samples post-dose will not be

performed. Before discharge, safety assessments post-dose on Day 1 will be completed and an Early Termination visit will be planned.

If a participant asks or decides to withdraw from the study, all efforts will be made to complete and report the observations, especially those related to the listed primary and secondary objectives, as thoroughly as possible up to the date of withdrawal. A clear and concise reason for withdrawal will be identified and recorded on the appropriate eCRF, along with the date of withdrawal.

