10.5. Treatment Compliance

The IP, CBL-514, will be administered at the study site by the designated study staff under guidance of Investigator or designee.

If a participant’s IP administration and site-related procedures are not conducted as defined in the protocol, the Investigator must make note of ensuring compliance to the protocol for future activities. The date and time of each IP administration and accompanying activity will be recorded in the eCRF. The number of syringes administered will be documented in the participant’s source documents.

A dosing compliance less than 90% or more than 110% of total dosage per treatment is a major deviation and may be deemed to have an influence on PK. Effort should be made to adhere to the study design. Compliance is defined as the dosage administered out of the total dose or number of injections out of the amount required per treatment in accordance with protocol.

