12.2.1. Day 1: Before Dosing

The following assessments will be carried out prior to the administration of IP unless otherwise noted¹:

- [REDACTED]
 - [REDACTED]
 - [REDACTED]
 - [REDACTED]
 - [REDACTED]
 - [REDACTED]
 - [REDACTED]
 - [REDACTED]
 - [REDACTED]
 - [REDACTED]
 - [REDACTED]
 - [REDACTED]
 - [REDACTED]
- [REDACTED]
 - [REDACTED]
 - [REDACTED]
 - [REDACTED]
 - [REDACTED]
 - [REDACTED]

¹ Available measurements of medical evaluations (body weight, abdominal fat thickness, physical examinations, and ECG) and laboratory evaluations (biochemistry, hematology, coagulation, and urinalysis) within 14 days prior to IP dose can be accepted as the Baseline value and will not necessitate duplicate examinations.

² If IP dose is within 7 days of Screening pregnancy test, pregnancy test on Day 1 will not be necessary to assess.

³ Blood samples for PK analysis will be collected from all 10 subjects. Of these 10 subjects, 6 subjects (the first 3 females and the first 3 males enrolled) will have additional blood samples collected for metabolite assessment.

— [REDACTED]
[REDACTED]
[REDACTED]

CBL-514 will be administered by assigned clinical staff. The IP administration should be completed within 60 minutes.

Participants will remain at the study site through to the completion of all scheduled post-dose procedures.

[illegible]

¹ Blood samples for PK analysis will be collected from all 10 subjects. Of these 10 subjects, 6 subjects (the first 3 females and the first 3 males enrolled) will have additional blood samples collected for metabolite assessment.

A participant who is withdrawn from the study due to a lack of dosing compliance will not continue with the collection of PK samples post-dose. Before discharge, physical examination, vital signs, and AE assessment will be performed, and a participant diary will be dispensed.

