16.2.1. Pharmacokinetic (PK) Population

The PK Population will consist of all participants who receive any amount of IP and have sufficiently evaluable concentration-time profiles of plasma curcumin and/or resveratrol to allow determination of at least one PK parameter among C_{max} , t_{max} , and AUC_{0-24hr} . An evaluable PK profile will be determined at the discretion of the pharmacokineticist following examination of participants with dosing or protocol deviations that could potentially affect the PK profile. The PK Population determination will be done by the study pharmacokineticist post database lock.

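### Stopping PK sampling in participants dosed outside 90–110% leaves the planned review of those deviations with essentially no post-dose data, and removing them ends adverse event collection early

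*Combined protocol and SAP*

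**What the plan says.** **Removal and sampling.** The Synopsis (Methodology) states that participants who do not meet Section 10.5 dosing compliance "will be withdrawn and will not continue the collection of PK samples post-dose". Section 9.6 makes that failure a ground for compulsory removal and adds: "The collection of PK samples post-dose will not be" performed. The after-dosing text of Section 12.2 repeats the rule for a participant withdrawn "due to a lack of dosing compliance will not continue with the collection of PK samples post-dose". Day 1 safety assessments are completed and an Early Termination (ET) visit is planned.

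**Compliance.** Section 10.5: "A dosing compliance less than 90% or more than 110% of total dosage per treatment is a major deviation", one that may influence PK. It continues: "Compliance is defined as the dosage administered out of the total dose or number of injections out of the amount required per treatment".

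**Analysis set.** Section 16.2.1: "The PK Population will consist of all participants who receive any amount of IP" and whose profile allows at least one of Cmax, tmax and AUC0-24hr to be determined. The pharmacokineticist decides evaluability, after database lock, having examined participants with dosing or protocol deviations.

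**Related text.** Section 8.4 wants participants with a stopping-criterion event kept in the study and followed. Section 9.5 lets the Sponsor recruit more participants to obtain an evaluable PK or Metabolite Population. Section 14.2 collects adverse events until the end-of-study call or ET visit. Section 16 makes no adjustment for missing data.

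**The concern.** Dosing is a single course on Day 1, so removal for dosing non-compliance stops no later treatment. What it stops is data collection. The analysis section plans a reasoned decision on whether a dosing deviation spoiled a profile, while the conduct sections ensure that, for the largest deviations, there is no profile to look at. The two parts of the plan cannot both work as written.

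Three things are at stake: PK (and possibly metabolite) profiles in a study of 10; the ability to see whether the lost participants differ from the rest; and scheduled safety follow-up in people who received an off-plan amount of product.

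**Working it through.** The plan gives no power, precision or non-compliance figure to reproduce. N = 10 is descriptive (Sections 8.2 and 16.1).

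**1. Who is affected.** The planned dose is 800 mg in 160 mL (Table 7).
- Band in mg: 0.90 × 800 = 720 to 1.10 × 800 = 880.
- Band in mL: 0.90 × 160 = 144 to 1.10 × 160 = 176.
- Illustration: 85% of the dose is 0.85 × 800 = 680 mg, and 680/320 = 2.1 times the highest dose for which the protocol reports PK (Sections 6.2.2.2 and 6.3). That participant would give no post-dose profile.

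**2. What would be available to examine.** Administration should finish within 60 minutes (Section 11.5), and the first post-dose sample is due 1 hour (± 10 minutes) from its start (Section 13.1). Non-compliance is therefore usually known at about the time of the first sample. Earlier median tmax was about 2 to 5 hours for curcumin and 4 to 5 hours for resveratrol (Section 6.2.2.2), so a pre-dose sample and perhaps a 1-hour sample would not describe the profile.

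**3. Provisions side by side.**
- Section 10.5 says a deviation outside the band *may* affect PK; Section 9.6 acts as if that were settled.
- Section 16.2.1 admits any amount of product given an evaluable profile; Section 9.6 prevents that profile from existing.
- For a participant who asks to withdraw, Section 9.6 seeks the fullest possible observations on the primary and secondary objectives up to withdrawal. A willing participant with an incomplete dose may not give the primary-endpoint samples.
- Section 8.4 keeps a participant with a stopping-criterion event in the study. If the same event cuts dosing below 90%, Section 9.6 removes that participant.

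**4. Safety follow-up.** The ET visit shares Visit 3 with Week 2 (Section 12.3), and collection ends there (Section 14.2), so the Week 4 call is lost. One adverse event of special interest, pigmentation change, is defined by lasting more than 4 weeks (Section 14.2.2).

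**5. Chance of losing profiles.** With non-compliance rate p (assumed), P(at least 1 of n) = 1 − (1 − p)^n. Expected profiles among the first 10 dosed are 10(1 − p), before any replacement.

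| Assumed p | Expected profiles | P(≥1 of 10 lost) | P(≥2 of 10 lost) | P(≥1 of 6 metabolite participants lost) |
|---|---|---|---|---|
| 2% | 9.8 | 0.18 | 0.02 | 0.11 |
| 5% | 9.5 | 0.40 | 0.09 | 0.27 |
| 10% | 9.0 | 0.65 | 0.26 | 0.47 |
| 20% | 8.0 | 0.89 | 0.62 | 0.74 |

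**6. Size of a selection effect, if there is one.** Suppose m of 10 are lost and their full-dose exposure would have been r times that of the rest (assumed). Retained geometric mean / all-10 geometric mean = r^(−m/10).
- m = 1: 0.978 at r = 1.25; 0.933 at r = 2 (2% to 7% low).
- m = 2: 0.956 at r = 1.25; 0.871 at r = 2 (4% to 13% low).

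The direction is also an assumption; with r below 1 the sign reverses.

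**7. Precision, for scale only.** The half-width of a 95% interval for a log-scale mean, in SD units, is t(0.975, n − 1)/√n: 2.262/√10 = 0.715, 2.306/√9 = 0.769, 2.365/√8 = 0.836. That is 7.5% wider with one loss and 17% wider with two, if nobody is replaced. The plan presents no such interval.

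**The case against.** The best defence is that the rule is deliberate. It is repeated consistently, the aim is PK at the maximal dose (Section 6.3), and Section 8.3 warns that administration deviations may affect PK. Section 16.2.1 also requires an evaluable profile, and its review still applies to smaller dosing deviations, overruns, sampling times and prohibited substances. Section 9.5 allows extra recruitment. This largely stands: it makes the problem one of reconciliation and supports a main summary limited to 90–110%. It does not justify withholding the samples, because a collected profile can be excluded later and an uncollected one cannot be recovered.

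A reader might infer more than the documents support:
- **That losses would be due to tolerability.** Injection site pain was common (50% in Cohorts 6–9, 100% in Phase 2a; Section 6.2.2.1), and Section 14.2.1.3 foresees interruption for the participant's safety. But those are reports of pain, not failures to complete dosing. Related reactions in Cohorts 6–9 were mild to moderate, and analgesia and anaesthesia are given. No rate, cause or link with exposure is stated.
- **That the highest exposures would go unmeasured through overdosing.** Exceeding 110% means more than 16 mL beyond the planned 160 mL. Nothing suggests this is likely.
- **That the two compliance measures disagree.** Injection volume and count are redacted; with a fixed volume per injection they could coincide. Only the lack of a governing measure is established.
- **That dose normalisation would solve the problem.** Resveratrol Cmax rose slightly less than proportionally, and its exposure tended to plateau from 240 to 320 mg (Section 6.2.2.2).
- **That safety follow-up stops altogether.** Injection site reactions are monitored to resolution or stabilisation (Section 14.1.4), and related events are followed (Section 14.3). What is lost is scheduled detection of new events after the ET visit.

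**Conclusion.** The point holds as an internal inconsistency that should be fixed before dosing. For dosing outside 720–880 mg, the examination planned in Section 16.2.1 has essentially no post-dose data, the Week 4 contact is lost, and Sections 8.4 and 9.6 conflict when one event triggers both.

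The numerical effect is modest unless losses are frequent. Under the assumed rates of 2% to 20%, the chance of losing at least one profile runs from 0.18 to 0.89. If losses were selective, the retained geometric mean would be about 2% to 13% low under the assumed ratios for one or two losses. Tolerability-driven selection is plausible for under-dosing but not shown. If it occurred, replacement would restore the count without removing it. Continued sampling would not correct the main summary either; it would let the lost participants be described.

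**What to change.** Reconcile the Synopsis, Section 9.6 and the after-dosing text of Section 12.2 with Sections 8.4, 10.5 and 16.2.1, separating dosing non-compliance from withdrawal from data collection.

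- Continue the already scheduled PK and metabolite samples and the Week 2 and Week 4 safety contacts in consenting participants who received any product. Leave the other withdrawal grounds in Section 9.6 as they are.
- Treat dosing outside 90–110% as a major deviation handled in analysis. Keep the main PK summary on participants within the band, and list the others individually with the dose actually injected.
- State in Table 10 that CL/F and Vz/F use the actual dose, and make sure that dose is captured in the eCRF. Label any dose-normalised Cmax or AUC as supportive, with a caution for resveratrol Cmax.
- State which compliance measure, dose or number of injections, governs.
- Report every lost profile with its reason.

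**Cost.** Protocol wording, possibly one eCRF field, and for each affected participant up to 11 scheduled post-dose draws (1, 2, 4, 5, 6, 7, 8, 10, 12, 18 and 24 hours) with assays and the overnight stay already planned. No enrolment is added, and the main summary gains no precision.
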